5.9 Data Management

5.9.1 Data Collection and Storage

Only IRB-approved study staff will have access to data collected for this research. Electronic data will be stored on Geisinger's secure network. Any hard copy data will be secured in a locked area. The following data, including relevant dates, will be collected:

- Names
- Medical record number
- Date of birth/date of death
- Information relevant to all encounters, admissions/discharges, clinical procedures, medications administered, problem list entries, device interrogations and lab values
- Baseline demographic variables of patients (age, sex, ethnicity, tobacco use, comorbidities)
- Clinical outcomes and procedural related complications

5.9.2 Records Retention

Records of data generated in the course of the study shall be retained for at least 6 years and could be used for future research studies submitted and approved by the IRB.

6 SAFETY MONITORING

6.1 Adverse Event Reporting

Clinical adverse events (AEs) will be monitored throughout the study. The date and time of onset and outcome, course, intensity, action taken, and causality to study treatment will be assessed by the study PI. In the event of a serious AE (SAE), this will be reported to the Geisinger IRB (GIRB) according to the GIRB guidelines.

Definitions:

An **adverse event** (AE) is any untoward, undesired, or unplanned event in the form of signs, symptoms, disease, or laboratory or physiologic observations occurring in a person given a test article or in a clinical study. The event does not need to be causally related to the test article or clinical study.

An AE includes, but is not limited to, the following:

- Any clinically significant worsening of a preexisting condition.
- An AE occurring from abuse (e.g., use for nonclinical reasons) of a test article.
- An AE that has been associated with the discontinuation of the use of a test article.

A **serious adverse event** (SAE) is an AE that:

- Results in death.
- Is **life-threatening** (see below).
- Requires inpatient hospitalization or prolongation of an existing **hospitalization** (see below).
- Results in a persistent or significant **disability** or incapacity (see below).
- Results in cancer.
- Results in a congenital anomaly or birth defect.
- Additionally, important medical events that may not result in death, be life-threatening, or require hospitalization may be considered SAEs when, based on appropriate medical judgment, they may jeopardize the subject and may require medical or surgical intervention to prevent one of the outcomes listed in this definition. Examples of such events include allergic bronchospasm requiring intensive treatment in an emergency

room or at home, blood dyscrasias or convulsions that do not result in hospitalization, or development of drug dependency or drug abuse.

Life-threatening refers to immediate risk of death as the event occurred per the reporter. A life-threatening experience does not include an experience, had it occurred in a more severe form, might have caused death, but as it actually occurred, did not create an immediate risk of death. For example, hepatitis that resolved without evidence of hepatic failure would not be considered life-threatening, even though hepatitis of a more severe nature can be fatal. Similarly, an allergic reaction resulting in angioedema of the face would not be life-threatening, even though angioedema of the larynx, allergic bronchospasm, or anaphylaxis can be fatal.

Hospitalization is official admission to a hospital. Hospitalization or prolongation of a hospitalization constitutes criteria for an AE to be serious; however, it is not in itself considered an SAE. In absence of an AE, a hospitalization or prolongation of a hospitalization should not be reported as an SAE by the participating investigator. This is the case in the following situations:

- The hospitalization or prolongation of hospitalization is needed for a procedure required by the protocol.
- The hospitalization or prolongation of hospitalization is part of a routine procedure followed by the center (e.g., stent removal after surgery). This should be recorded in the study file.

In addition, a hospitalization for a preexisting condition that has not worsened does not constitute an SAE.

Disability is defined as a substantial disruption in a person's ability to conduct normal life functions.

If there is any doubt about whether the information constitutes an SAE, the information is treated as an SAE.

A protocol-related adverse event is an AE occurring during a clinical study that is not related to the test article but is considered by the investigator or the medical monitor (or designee) to be related to the research conditions, i.e., related to the fact that a subject is participating in the study. For example, a protocol-related AE may be an untoward event occurring during a washout period or an event related to a medical procedure required by the protocol.

Other Reportable Information. Certain information, although not considered an SAE, must be recorded, reported, and followed up as indicated for an SAE. This includes:

- Pregnancy exposure to a test article, except for exposure to prenatal vitamins. If a pregnancy is confirmed, use of the test article must be discontinued immediately. Information about pregnancy exposure includes the entire course of pregnancy and delivery, and perinatal and neonatal outcomes, even if there are no abnormal findings. Both maternal and paternal exposure are considered other reportable information. For exposure involving the female partner of a male subject, the necessary information must be collected from the subject, while respecting the confidentiality of the partner.
- Lactation exposure to a test article with or without an AE.
- Overdose of a test article as specified in this protocol with or without an AE. Baby formula overdoses without any AEs are excluded.
- Inadvertent or accidental exposure to a test article with or without an AE.

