5 STUDY DESIGN

5.1 Description

This is a randomized, prospective, single-blinded trial. Patients will be randomized to HOT-CRT versus BVP and will remain blinded to their treatment allocation. Both treatment options use standard-of-care, FDA-approved devices. The distinction is only in the allocation toward HOT-CRT and BVP. Treating physicians will be aware of assignment in order to facilitate routine device follow-up. Echocardiographic evaluation will also be performed in a blinded manner. Study physicians with the role of completing this evaluation will be blinded to lead placement.

Crossover is permitted between treatment group allocation if:

- CS lead (BVP) cannot be placed due to difficult cannulation of the CS, limited branches at the posterolateral or lateral wall, or phrenic nerve capture. These patients may then crossover to HOT-CRT. All efforts will be made to achieve CRT using CS lead.
- HOT-CRT patients may crossover if HPCSP lead cannot be positioned with adequate stability and reasonable pacing output and acceptable electrical resynchronization cannot be achieved.

Implant procedure will be per routine percutaneous access, as is standard for pacemaker and implantable cardioverter defibrillators (ICDs). All patients will receive FDA-approved cardiac resynchronization therapy pacemaker or defibrillator device, as per standard of care outlined for the patient.

Follow-up will be performed at 2 weeks post-implant for incision check and device interrogation, as is standard of care. In addition, routine device and clinical follow-up will be scheduled at 3, and 6 months, with remote device monitoring between scheduled visits, as needed.

Electrocardiography (i.e., ECG) will be performed pre-implant, prior to hospital discharge, and at 3- and 6-months post-discharge, as is standard of care. Echocardiography will be performed pre-implant, at 6 months to evaluate for change in left ventricular ejection fraction (LVEF), chamber dimension, and wall motion with strain imaging as is standard of care in the treatment of patients with advanced heart failure. NYHA functional class and quality of life, as measured

by the Kansas City Cardiomyopathy Questionnaire (KCCQ) and the EuroQoL 5D (EQ-5D), will be assessed pre-implant and at 6 months.

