5.2 Study Population

Target Population: Patients with heart failure (HF) eligible for CRT as part of routine standard-of-care based on accepted Class I or Class II indications will be considered for this study.

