5.2.2 Inclusion Criteria

Eligible patients will be similar to those previously enrolled in the large randomized controlled trials and current Society guidelines^{18, 19} which support current indications for CRT. The following are the inclusion criteria for the HOT-CRT study:

1. Patients at least 18 years of age
2. Diagnosis is NYHA Class II, III, and ambulatory Class IV heart failure with either ischemic or nonischemic cardiomyopathy and patients with NYHA Class I symptoms and ischemic cardiomyopathy, with at least one of the following:
 - i. LV systolic dysfunction with LVEF \leq 35% and Evidence of bundle branch block with QRS duration $>$ 120 msec
 - ii. LV systolic dysfunction with LVEF \leq 50% and with need for $>$ 40% RV pacing

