5.5 Procedures & Study Timeline

Patients enrolled in the study will receive a permanent CIED (CRT-pacemaker or CRT-defibrillator) as clinically indicated. Patients will be centrally randomized by the study team with input from the biostatistician.

Procedure:

Patients randomized to biventricular pacing will undergo left ventricular lead placement in the coronary sinus venous branches.

Patients randomized to HOT-CRT will undergo CRT as described below. His bundle pacing lead will be placed initially to achieve CRT. If complete resynchronization is achieved (BBB normalization) but capture thresholds are high (1.5-2V), the lead may be placed in the distal conduction system (left bundle branch area). If only partial QRS narrowing is achieved, a coronary sinus lead may be placed and LV timing may be optimized to achieve maximal resynchronization. This will be at the discretion of the implanting physician.

Visit One - Pre-Implant

Enrolled subjects will undergo the following standard care procedures, unless noted as being completed for research purposes:

1. Clinical physical evaluation
2. Serum or urine pregnancy screen for women of child-bearing potential
3. Serum BNP or pro-BNP, baseline metabolic panel
4. Electrocardiogram
5. Transthoracic Echocardiogram (TEE) will be completed if it has not been done within the previous 3 months prior to Visit One.
6. Kansas City Cardiomyopathy Questionnaire (KCCQ) will be completed by the subject as part of the study
7. EuroQoL 5D (EQ-5D) will be completed by the subject as part of the study
8. Six Minute Walk Test (6MWT) will be administered by study staff to record distance as part of the study
9. NYHA functional class
10. Randomization – Subjects will be randomized by study staff in the study REDCap database to either HOT-CRT or standard BVP lead placement using a permuted block design. Patients will be blinded to randomization arm. Blocks of size 2 and 4 will be

randomly generated. Randomization will be stratified by LBBB and non-LBBB (right bundle branch block, RV pacing or narrow QRS) and by clinical site.

11. Collection of adverse events from time of consent until end of study participation

Visit Two – Day of Implant

1. Implant completed according to the assigned randomization arm by investigator
2. Electrocardiogram completed pre/post procedure
3. Device interrogation completed prior to hospital discharge
4. Adverse event collection

Visit Three – 2-week follow-up

1. Device Interrogation

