5.5.1 Participant Withdrawal

Subjects will be free to withdraw from the study at any time by notifying the study team in writing. If the subject withdraws, no further data will be collected after that timepoint unless needed for safety reporting.

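### A leftover template sentence on pregnancy, read literally, orders staff to stop a permanent, clinically indicated CRT device

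*Combined protocol and SAP*

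**What the plan says.** The pregnancy bullet under Other Reportable Information in Section 6.1 contains this rule: "If a pregnancy is confirmed, use of the test article must be discontinued immediately." It has no exception for an implanted device, and Section 6 does not say what the test article is.

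Elsewhere the protocol describes the treatment:

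- Section 5.1, on both arms: "Both treatment options use standard-of-care, FDA-approved devices."
- Section 5.1, on what is implanted: "All patients will receive FDA-approved cardiac resynchronization therapy pacemaker or defibrillator device, as per standard of care outlined for the patient."
- Section 5.5: "Patients enrolled in the study will receive a permanent CIED (CRT-pacemaker or CRT-defibrillator) as clinically indicated."
- Section 5.2, on the target population: patients "eligible for CRT as part of routine standard-of-care based on accepted Class I or Class II indications."
- Section 5.2.2: one entry route is a reduced ejection fraction "with need for $>$ 40% RV pacing."

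On pregnancy itself, Section 5.2.3 makes it an exclusion, and Visit One in Section 5.5 lists a "Serum or urine pregnancy screen for women of child-bearing potential." No later visit lists a pregnancy test or a rule for a pregnancy that begins after implant.

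**The concern.** The sentence suits a drug or a nutritional product, which can be stopped at once. It does not suit a permanent pacing system that the patient would have been offered outside the trial. The wording is mandatory and immediate, so it leaves the clinician no discretion. Taken at its word, it means switching off or removing resynchronization pacing, or defibrillator protection, in a pregnant woman with heart failure, some of whose peers entered because they depend on frequent ventricular pacing.

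Much leftover template text is harmless because it triggers nothing. This sentence directs an action on treatment. An investigator who gave proper care would have to depart from a mandatory line of the protocol to do so.

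**Working it through.** The plan states no figure on this point, so there is none to reproduce. The check is mainly one of reading, followed by a rough estimate of how often the situation could arise.

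**Reading**

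1. *What could the test article be?* Section 6.1 uses the term repeatedly without defining it. The trial supplies a CRT pacemaker or defibrillator and its leads, and nothing else. On the broad reading, the term means the whole system. On the narrow reading, it means only the conduction-system lead or the HOT-CRT allocation. The broad reading stops all device therapy. The narrow one either still stops pacing from an implanted lead or has nothing left to act on, because allocation is finished at implant. No reading yields a sensible instruction.
2. *Does another section override it?* The exclusion in 5.2.3 and the screen at Visit One apply before implant. Section 5.5.1 reads: "Subjects will be free to withdraw from the study at any time by notifying the study team in writing." It then ends data collection, and it is silent on the device. Section 6.1 mentions discontinuation elsewhere only as part of the definition of an adverse event. The pregnancy sentence is therefore the only instruction in the protocol to stop treatment.
3. *Where did it come from?* The same list exempts prenatal vitamins and excludes certain baby-formula overdoses. Neither has any place in a device trial, which points to a drug or nutrition template.

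**Frequency**

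Inputs from the documents: about 100 participants (5.2.1) and about 6 months of participation each (5.4.1).

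Exposure = 100 × 0.5 years = 50 person-years.

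The documents give no age or sex mix and no pregnancy rate. The next two inputs are assumptions: the share of participants who could become pregnant (5% to 15%), and their yearly pregnancy rate (1% to 5%).

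| | Share | Yearly rate | Expected pregnancies | Chance of at least one (Poisson) |
|---|---|---|---|---|
| Low | 0.05 | 0.01 | 50 × 0.05 × 0.01 = 0.025 | 1 − exp(−0.025) = 0.025 |
| High | 0.15 | 0.05 | 50 × 0.15 × 0.05 = 0.375 | 1 − exp(−0.375) = 0.313 |

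The 50 person-years slightly overstate the time at risk after implant, because participation is counted from consent.

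**The case against.** The strongest reply is that this is housekeeping. The sentence sits in a reporting list, not in the design, procedures or withdrawal sections, and no visit procedure carries it out. The term is undefined, so applying it to the CRT system is the reader's inference. Sections 5.1 and 5.5 already tie device care to standard of care and clinical indication, and no competent clinician would switch off a needed device because of a line written for another kind of product. The frequency range is about fifteenfold in expected events, rests on assumed inputs, and counts pregnancies, not wrongly stopped devices. Deletion alone would be enough.

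Much of this stands. The practical risk is low, the template origin is plain, and the upper figure of 31% comes from the most generous inputs and must not be read as a probability of harm. This is a drafting slip, not a decision about the design.

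Three things do not follow. The location does not change the wording, which is a directive; the duty to report stands without it. An undefined term does not rescue the sentence, because the alternative readings leave it either empty or still wrong. And the general statements on standard of care do not address pregnancy, so the one sentence that does is the specific rule and points the other way.

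**Conclusion.** The concern holds, as a minor point. The sentence is current, mandatory text, and applied to this trial's only study treatment it is a wrong rule. That conclusion is textual and does not depend on the frequency estimate.

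The situation is expected to be rare: 0.025 to 0.375 participant pregnancies over the whole trial under the assumed share and rate, or a 2.5% to 31% chance of at least one. Harm would also require someone to act on the sentence, which is unlikely and which the documents give no means of estimating. Endpoints, sample size, analysis and adverse-event collection are not affected.

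**What to change.** Delete the discontinuation sentence from the pregnancy bullet in Section 6.1. Keep the rest of the bullet that concerns reporting and follow-up of the pregnancy and its outcome. Add one line, for example:

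> If a participant becomes pregnant after implant, device therapy continues and is managed by the treating clinician as clinically indicated.

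Deletion removes the error. The added line fills the gap that deletion leaves and agrees with Sections 5.1 and 5.5.

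The cost is one sentence removed and one added in the protocol. Visits, data collection, sample size and analysis stay as they are.

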6.2 Recording and Reporting

A subject's AEs and SAEs will be recorded and reported from the signing of the informed consent form to conclusion of patient follow-up in accordance with GIRB policy guidelines.

6.3 Serious Adverse Event Reporting

The PI will notify GIRB of all study SAEs in accordance with policy guidelines. If an SAE has not resolved at the time of the initial report, a follow-up report including all relevant new or reassessed information (e.g., concomitant medication, medical history) will be submitted to GIRB. An SAE will be followed until either resolved or stabilized.

7 PROTECTION OF HUMAN SUBJECTS

7.1 Informed Consent and HIPAA Authorization

The investigator will provide for the protection of the subjects by following all applicable regulations. The informed consent/authorization form will be submitted to the IRB for review and approval.

Before any procedures specified in this protocol are performed, a subject must:

- Be informed of all pertinent aspects of the study and all elements of informed consent.
- Be given time to ask questions and time to consider the decision to participate.
- Voluntarily agree to participate in the study.

- Sign and date an IRB-approved informed consent form.

7.2 Potential Risks/Benefits and Protection of Human Subjects Against Risks

Potential Risks

Risks associated with both CS lead position and HBP which include, but are not limited to, the risk for cardiac perforation, tamponade, lead dislodgement, fracture, and site infections. Early data indicate that the two technologies are comparable with respect to risk profile.

All electronic study data will be kept in password-protected computer files and hard copy data will be stored in a locked environment that is only accessible only to the study team members. Data will be coded by linking a unique study identification number to patients' medical record numbers. Analysis will be performed using the coded data. Only aggregate data without personal identifiers will be included when presenting results or submitting manuscripts for publication.

Benefits

There will be no direct benefit to patients who are included in this study. We hope that what is learned from this study will help others in the future.

